1. SYNOPSIS

The elderly patient demented in an acute geriatric department: pilot study, monocentric, randomized on the use of aromatherapy as a complementary treatment tool to psychopharmacology in psychological disorders and behavior (BPSD).

Rationale

Behavioral and psycological symptoms of dementia (BPSD) are a big issue for families, paramedics, physician and the patient itself (1,2,3,4).

In absence of universally recognized guidelines, the standard of treatment of these disorders involves the use of psychotropic drugs (typical/atypical neuroleptics, antidepressants, benzodiazepines) that are often found to have a reduce efficacy and induce a number of side effects such as sedation, impaired motor neurons slowdown, cardiac electrical alterations and extrapyramidal syndrome (5,6,7,8,9). In consideration of this, it is important to check for treating alternative ways, which can reduce psychological and behavioural disorders and at the same time can reduce the use of psychotropic drugs.

Concerning the aromatherapy [10], the therapeutic use of natural essential oils, there are decades of clinical experience, especially in France, accompanied by increasing scientific evidence with significant increase in publications regarding its use of psychological disorders and dementia-related behavior context (11,12,13,14).

Based on the available scientific publications, it has been therefore decided to use two essential oils (*Citrus sinensis, Lavandula angustifolia*) in environmental diffusion within the Geriatric Department of the Clinic Luganese Moncucco.

Objectives

Primary objectives: through the execution of the Neuropsychiatric Inventory – Nursing Home Version (NPI-NH), the neuropsychiatric and psychopathological symptoms of dementia patients will be evaluated in order to assess how the use of aromatherapy can improve the management of BPSD, reducing, where there is clinical indication, psychotropic therapy and secondary side effects. The score is considered positive if the presence of BPSD is greater than or equal to 1 (15, 16,17); the improvement of the score is represented from decrease of the NPI-NH respect to the initial assessment (19, 20).Performing neuropsychological tests is not an additional attention to enrolled patients, but it is part of clinical practice (18).

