6. PROJECT OBJECTIVES

The goal of this project is to evaluate the effectiveness of aromatherapy in air diffusion in addition to psychotropic drugs in order to evaluate a possible reduction in BPSD.

The project's hypothesis is that GROUP B patients show an improvement in their BPSD. The performed neuropsychological tests will provide the answer to the project hypotesis.

Primary objectives: validate the hypothesis that the use of aromatherapy in air diffusion can improve the BPSD management, allowing a reduce in psychotropic therapy prescribed and its secondary side effects. The patient's nurses will be tested with NPI-NH, that will characterize

frequency and seriousness of BPSD [15,16, 17]. A score greater or equal to 1 is considered positive for presence of BPSD.

Secondary objectives: validate the hypothesis that the use of aromatherapy will improve the management of BPSD patients, with a simultaneously reduction of physicians, nurses and care assistants stress. The last aspect will be evaluated with a specific part of NPI-NH test. The decrease of the initial score represented an improvement [19.20]. The NPI-NH test will be performed according to the time points defined in paragraph 7.1.1

The obtained results could be interesting to the future implementation of the use of essential oils in air diffusion in acute geriatric departments and in all facilities with BPSD patients.

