7. RANDOMIZATION

Enrolled patients with BPSD will be randomized according to the following randomization scheme (AABB, ABAB, BBAA, BABA, ABBA, BAAB).

A repetition of the first 4blocks will be performed, for a total of 32 patients, 16 each group, according to the following scheme:

AABB, ABAB, BBAA, BABA AABB, ABAB, BBAA, BABA

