8. PROJECT DESIGN

The project will be managed in the acute geriatric department of the Clinica Luganese Moncucco. Enrolment and treatment scheme is present in the flow chart (chapter 2).

After randomization patients will be enrolled in the two groups GROUP A, control group, and GROUP B, treatment group.

The enrollment will be performed in 2 months.

GROUP A: 16 patients, following the inclusion criteria, will be enroll and they will be treated with psychotropic drugs.

GROUP B: 16 patients, following the inclusion criteria, will be enroll and they will be treated with psychotropic drugs and, in a complementary way, with aromatherapy in environmental diffusion.

The project hypothesis will be validated using the following neuropsychological and functional tests:

- CAM (Confusion Assessment Method);
- CDR (Clinical Dementia Rating Score)
- MMSE (Mini Mental State Examination);
- FAB (Frontal Assessment Battery);

- Tinetti's scale;
- BADL (Basic Activities of Daily Living);
- IADL (Instrumental Activities of Daily Living);
- NPI-NH (Neuropsychiatric Inventory Nursing Home Version);

Neuropsychological tests are part of clinical practice [18].

Scientific reports show that essential oils in air diffusion are effective in 3 days. A final timepoints of 14 days represent the mean hospital stay:

2 days for the collection of behavioral data;

6 days to observe the possible effectiveness of aromatherapy in air diffusion;

6 days to adapt the therapy with oils and psychotropic drugs and stabilize patient's condition for a possible discharge.

Enrolled patients and nurses will be tested according to the following times:

8.1.1 Observation for 48 hours with data collection and execution of the NPI-NH (T1): in the 48 hours after patient admission at the Geriatric Department or at the diagnosis of dementia, the information collection will be performed: sensitive data (age, gender), dementia condition (CAM, CDR, MMSE, FAB), functional status (IADL, BADL, Tinetti scale) and the used number of psychotropic drugs. As a result of this evaluation, patient will be assessed for the presence of BPSD using the NPI-NH assessment scale, nurses will be undergo to NPI – NH test within 48 hours after patient admission. In case of a score greater than or equal to 1, patient will be followed within the study project, otherwise it will follow the standard process.

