21.1.7 Neuropsychiatric Inventory NPI-NH

NPI-NH	Neuropsychiatric Inventory – Nursing Home Version Scoring Summary						
CENTER # SCREENING	# PATIENT #	PATIENT INITIALS	VISIT	DATE			
		F M L					
Please transcribe appropriate cate	gories from the NPI-NH Work	sheet into the boxe	s provided.				
For each domain: - - If symptoms of a domain did not apply, check the "N/A" box. - - If symptoms of a domain were absent, check the "0" box. - - If symptoms of a domain were present, check one score each for Frequency and Severity. - - Multiply Frequency score x Severity score and enter the product in the space provided. - - Total all Frequency x Severity scores and record the Total Score below. - - If symptoms of a domain were present, check one score for Occupational Disruptiveness; total all occupational disruptiveness scores for a summary score.							

DOMAIN	N/A ¹	ABSENT	FREQUENCY	SEVERITY	FREQUENCY X SEVERITY	OCUPATIONAL DISRUPTIVENESS
		0	1 2 3 4	123		0 1 2 3 4 5
A. Delusions						
B. Hallucinations						
C. Agitation/Aggression						
D. Depression/Dysphoria						
E. Anxiety						
F. Elation/Euphoria						
G. Apathy/Indifference						
H. Disinhibition						
I. Irritability/Lability						
J. Aberrant Motor Behavior						
TOTAL SCORE:						
K. Sleep and Nighttime Behavior Disorders						
L. Appetite/Eating Changes						

Neuropsychiatric Inventory – Nursing Home Version

Worksheet

Directions: Read all items from the NPI-NH "Instructions for Administration of the NPI-NH". Mark Caregiver's responses on this worksheet before scoring the Frequency, Severity, and Occupational Disruptiveness.

A. DELUSIONS: DYes No N/A Frequency Severity Occupational Disruptiveness D. Fear of harm 2. Fear of theft 3. Spousal affair 4. Phantom boarder 5. Spouse imposter 6. House not home 7. Fear of abandonment 8. Talks to TV, etc. 9. Other	B. HALLUCINATIONS:YesNoN/A Frequency Severity Occupational Disruptiveness 1. Hears voices 2. Talks to people not there 3. Sees things not there 4. Smells things not there 5. Feels things not there 6. Unusual taste sensations 7. Other
C. AGITATION/AGGRESSION: DYes No N/A FrequencySeverity Occupational Disruptiveness 1. Upset with caregiver; resists ADL's 2. Stubbornness 3. Uncooperative; resists help 4. Hard to handle 5. Cursing or shouting angrily 6. Slams doors; kicks, throws things 7. Hits, harms others 8. Other	D. DEPRESSION/DYSPHORIA: Description Of the second

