## Statistical methodology

The Mann-Whitney test has been used to evaluate the statistical significance of the difference between the variations in scores (T3 - T1) regarding the two interest groups of patients (control and treated). The Mann-Whitney test has been used instead of the t-test for independent samples as the scores variations distributions between T1 and T3 are not Gaussian, with the exception of the "thymic" area.

The statistical significance of the differences between the variations in scores  $(T_3 - T_1)$  has been further explored using a linear regression model to account for the initial CIRS comorbidity index (that resulted slightly higher in the control group); it should be noted that Huber-Sandwich robust standard errors have been used because of the presence of heteroskedasticity. Moreover, because of the relatively reduced number of observations available, the estimate has been repeated using the median regression model to check the robustness of the results. Both estimates (not presented here for convenience) confirmed the results obtained with the Mann-Whitney test.

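### Area-level T3−T1 comparisons include patients who score 0 in the area at T1 and cannot improve there: the Mann-Whitney test stays valid but is diluted, and median regression cannot confirm it where most changes are 0 in each arm

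*SAP*

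**What the plan says.** **Entry.** Protocol section 8.1.1 sets the threshold: "In case of a score greater than or equal to 1, patient will be followed within the study project". Section 6 uses the same cut-off: "A score greater or equal to 1 is considered positive for presence of BPSD". Neither sets a minimum for a single domain or group of domains.

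**Scoring.** The NPI-NH form (Protocol 21.1.7) has twelve domains, A to L. A present domain scores frequency (1 to 4) times severity (1 to 3), so 1 to 12. For an absent one the instruction begins "If symptoms of a domain were absent, check the" and points to the zero box. The form then says "Total all Frequency x Severity scores and record the Total Score below". The total row follows domains A to J, with K (sleep) and L (appetite) below it.

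**Direction of benefit.** The Protocol synopsis states that "the improvement of the score is represented from decrease of the NPI-NH respect to the initial assessment".

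**Analysis.** The SAP (Statistical methodology) compares T3−T1 changes between arms by Mann-Whitney test because the changes "are not Gaussian, with the exception of the 'thymic' area". It then fits a linear regression with robust standard errors, adjusting for CIRS, and "the estimate has been repeated using the median regression model to check the robustness of the results". It reports that both fits agreed with the Mann-Whitney test but does not show them. The SAP text does not define the areas, does not use the T1 area score, and does not say how patients at 0 in an area are handled.

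**The concern.** A patient who scores 0 in an area at T1 can only stay at 0 or worsen there. Improvement, as the protocol defines it, is out of reach for that patient in that area. Pooled with the rest, such patients add a block of tied zero changes to both arms.

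This has two consequences. First, the area effect shrinks towards 0 in proportion to the share of patients without the symptom, and the rank test loses power. Areas with different shares at 0 are then hard to compare. Second, if zeros are the majority in each arm, both arm medians are 0, and a median regression returns 0 for treatment even when the patients who had the symptom improved. Agreement or disagreement of that fit with the main test then carries no information. With 16 patients per arm there is little power to spare.

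**Working it through.** **Inputs from the documents.** 16 patients per arm (Protocol section 7: "for a total of 32 patients, 16 each group"); entry at a score of 1 or more; domain score 0 if absent and 1 to 12 if present; endpoint T3−T1; adjustment for CIRS only. The documents state no power, effect size or standard deviation, so there is no planned figure to reproduce.

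**Assumptions, not in the documents.** The share q of patients above 0 in the area at T1, and the effect among them.

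**Step 1, dilution.** If patients at 0 do not change, the all-patient mean difference is q × (difference among patients with the symptom). With an assumed difference of −2.6 points:
- q = 0.7: 0.7 × −2.6 = −1.8
- q = 0.5: 0.5 × −2.6 = −1.3
- q = 0.3: 0.3 × −2.6 = −0.8

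**Step 2, power in a one-domain area.** Assumed model A: latent mean change −1 (control) v −5 (treated), SD 3, scores held within 0 to 12, 10% new onset among patients at 0. Assumed model B: treated patients keep on average 40% and controls 90% of their T1 score, and nobody at 0 worsens.

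| Share at 0 at T1 | A: plain Mann-Whitney | A: van Elteren, stratified by 0 v ≥1 | B: plain, all patients | B: patients ≥1 only |
|---|---|---|---|---|
| 30% | 51% | 61% | 61% | 73% |
| 50% | 30% | 39% | 43% | 55% |
| 70% | 15% | 17% | 22% | 28% |

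Under model B, power is 90% when nobody is at 0. At 80% at 0, restricting to patients with the symptom gains nothing (11% v 13%). With no treatment effect, the plain and stratified tests both reject in about 4 to 5% of trials.

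**Step 3, when the median regression is stuck at 0.** Without covariates, the treatment coefficient is the difference between the arm medians. If at least 9 of 16 changes are 0 in each arm, both medians are 0 and so is the coefficient. With one unrelated covariate standing in for CIRS, 99 to 100% of simulated trials with such majorities gave exactly 0. Worked examples, with all controls unchanged:
- 7 of 16 treated patients fall by 3, 4, 5, 6, 7, 8 and 9 points. The mean difference is −42/16 = −2.6 and Mann-Whitney p = 0.004. The coefficient was 0 in all 300 CIRS draws.
- 9 of 16 treated patients fall. Now 23/32 = 72% of all changes are 0, but only 7 of 16 in the treated arm. The coefficient was never 0.

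The condition is therefore a zero majority within each arm, not a zero majority overall.

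**Step 4, how often that could arise.** The chance that at least 9 of 16 patients score 0 at T1 in one arm is 0.026, 0.402 and 0.926 at q = 0.7, 0.5 and 0.3. In both arms it is the square: 0.1%, 16% and 86%. Exact zero coefficients were more frequent than this, because some patients with the symptom also do not change. For a one-domain area with 30%, 50% and 70% at 0 they were 10%, 51% and 93% of trials under model A, and 15%, 65% and 98% under model B.

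**Step 5, areas that pool domains.** If domains are independent and each is absent with probability z, the share at 0 in the area is z² for two domains and z³ for three. For z = 0.3, 0.5 and 0.7 that is 9%, 25% and 49%, or 3%, 12.5% and 34%. Exact zero coefficients under model A fell to 1%, 3% and 47% with two domains and 1%, 1% and 23% with three. Stratifying still gained power, by 1 to 10 points.

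**The case against.** The other side has good arguments.

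- **The test is not wrong.** The all-patient Mann-Whitney test holds its error rate and compares randomised arms. Patients at 0 can still worsen, so they carry some information. An effect among patients with the symptom is a different estimand, not a correction. This stands: a reader might infer that the reported test is invalid or biased, and neither the documents nor the calculations support that.
- **The only area named points the other way.** The SAP describes the thymic changes as Gaussian, which does not suit a large block of zeros. This stands for that area. It does not settle the others, where departure from normality could come from zeros or from plain skew.
- **Areas may pool domains.** They are undefined, and pooling reduces the problem sharply (step 5). This stands as a limit on size.
- **The regressions may not have been run by area, and a linear regression is also reported.** Both are fair. A reader might infer that the SAP's statement of agreement is empty. The documents do not show that; they only leave it impossible to check.
- **A general ban on median regression wherever half of all changes are 0 would go too far.** This stands: the example with 72% zeros overall gave an informative fit.
- **The protocol planned descriptive analysis only, and its objectives use the NPI-NH score rather than areas.** This limits the weight of the point but does not remove it, because the SAP reports significance tests.

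**Conclusion.** The point holds in a limited form. One NPI-NH point is enough for entry, so patients can be at 0 in an area at T1, and the SAP text makes no use of the T1 area score. Area-level Mann-Whitney results are valid but diluted. Under the assumed effects, the power that stratifying would recover is about 2 to 10 points for a one-domain area and 1 to 10 for pooled areas. The actual loss cannot be derived, because the documents give neither the areas nor the share at 0. The total score is little affected, since entry requires at least one point; K and L may not count towards that total.

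Median regression cannot confirm an area result where more than half of the changes are 0 in each arm. That is likely for single-domain areas with many patients at 0 and uncommon for areas pooling several frequent domains. Whether it happened in this trial is unknown.

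**What to change.** 1. Define each area by its NPI-NH domains. For each, add a van Elteren test stratified by T1 area score 0 v ≥1, keeping all randomised patients. The SAP is written with results known, so label it a sensitivity analysis and keep the reported Mann-Whitney test beside it.
2. For each area and arm, report the number at 0 at T1 and the number with new symptoms (0 at T1, ≥1 at T3). As a supplementary estimate, give the T3−T1 difference between arms with a confidence interval among patients with area score ≥1 at T1.
3. Show the median-regression estimates with the share of zero changes per arm. Do not cite them as confirmation for any area where that share exceeds half in each arm.
4. Form the strata only from T1 scores taken before allocation. Protocol section 5 does not list the NPI-NH among the tests done before randomisation, while section 8.1.1 makes it a condition of follow-up, so the SAP should state the actual order.

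The cost is SAP wording and a modest re-run on data already collected. The drawback is small numbers in the subset: with 30% to 70% at 0, about 11 down to 5 patients per arm (16 × 0.7 = 11.2; 16 × 0.3 = 4.8). Those counts must be shown.

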
Nurses will be undergo to NPI – NH test within 48 hours after patient admission or at first appearance of BPSD **(T1), T2 (T1-3 days)** 3 days after enrollment, at **T3 (T1-6 days)** 6 days after enrollment, at **T4 (T1-12 days)** at 14th day. According to the same timing, NPI-NH will also be performed to the resident physicians, the nurses and the care assistants to assess the psychological distress. The NPI-NH test will be performed following the Good Clinical Practice.

The tests results performed to the two groups of patients will be considered in order to assess a possible reduction in BPSD. As the project is a pilot study, a descriptive analysis will be performed.

Here the schemes defined for treatment with aromatherapy and psychotropic drugs, according to scientific publications in the first case and scientific publications and Evidence Based Medicine in the second:

Aromatherapy

Route of administration: air diffusion with ultrasonic diffuser in a single room and for about an hour.

Doses:

- Citrus sinensis: 6 drops at 8, 12 and 18 in nebulization

and

- Lavender angustifolia: 6 drops 8 p.m. in nebulization

PRN PSYCOPHARMACOTHERAPY

Drug:

- in case of psychomotor agitation:

Haloperidol 1 mg PO 10 times in 24 hours

1 mg SC/IM 5 times in 24 hours

Reperidone 0.5mg - 2mg PO in 24 hours *Olanzapine* 2.5 mg – 5 mg PO in 24 hours

Clozapine 6.25 mg – 25 mg PO in 24 hours

Quetiapine 12.5mg - 150mg PO in 24 hours

- in case of sleep disturbance:

Valerian 1 tb - 2 tbs PO in 24 hours Melatonin 1 tb - 2 tbs PO in 24 hours Lorazepam 0.5 mg - 3mg PO in 24 hours Oxazepam 7.5mg - 45mg PO in 24 hours Clomethiazole 1 tb -3 tbs PO in 24 hours - in case of anxiety/depression: Trazodone 25 mg – 150 mg PO in 24 hours Escitalopram 10 mg – 20 mg PO in 24 hours Mirtazapine 15 mg – 45 mg PO in 24 hours

Citalopram 10 mg - 20 mg PO in 24 hours

Paroxetine 20 mg – 50 mg PO in 24 hours

The control group is treated with psychopharmacological therapy, defined by the PI, according to the Evidence Based Medicine criteria.

Patient can withdraw the ICF at any time.

The investigators could decide to withdraw a patient for safety and health.

The withdrawn patients will not be evaluated unless they have been treated for 8 days, useful to evaluate the aromatherapy efficacy.

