8.1.2 Assessment of NPI-NH at T2 (T1-3 days): 3 days after enrollment, patient will be re-evaluated with NPI-NH to assess BPSD progress. In addition, the distress level of on the three health caregivers is also measured with the NPI-NH test.

8.1.3 Assessment of NPI-NH at T3, assessment of vital parameters and use of drug reserves (T1-6 days): 6 days after enrollment, NPI-NH will be re-executed, with associated assessment of patient's vital signs (PAS, PAM, FC) and the use of psychotropic drug reserves.

8.1.4 Final T4 assessment (T1-12 days): NPI-NH scale will be performed in association with vital signs.

The physician in charge of dispensing the NPI-NH questionnaires to nurses to collect BPSD patients status, will also submit the questionnaires to the referring physician, nurse and care assistants with the aim to assess the level of stress in the clinical staff (see "Distress" column in NPI-NH questionnaire in the appendix).

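### The SAP's regressions of the T3-T1 change name only CIRS as a covariate; adding the T1 value of the same score, and showing the estimates, would usually give a more precise result

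*SAP*

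**What the plan says.** The SAP's only methodology section is written in the past tense. Its main comparison is on change: "The Mann-Whitney test has been used to evaluate the statistical significance of the difference between the variations in scores", taken as T3 minus T1, control against treated. It reports that the changes were not Gaussian except in the thymic area, so at least some of the analysed scores are area scores and not only a total.

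The result is then explored with a linear regression with robust standard errors "to account for the initial CIRS comorbidity index (that resulted slightly higher in the control group"). A median regression follows as a robustness check, "because of the relatively reduced number of observations available". No other covariate is named for either model. On results, the section says: "Both estimates (not presented here for convenience) confirmed the results obtained with the Mann-Whitney test".

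In the protocol, section 8.1.1 lists the T1 data besides age and gender as "dementia condition (CAM, CDR, MMSE, FAB), functional status (IADL, BADL, Tinetti scale) and the used number of psychotropic drugs", followed by the NPI-NH. CIRS is not in that list, nor among the scales in the appendix (section 21.1). Entry depends on the T1 NPI-NH: "In case of a score greater than or equal to 1, patient will be followed within the study project". Section 8.1.3 sets T3: "6 days after enrollment, NPI-NH will be re-executed". Section 13 plans descriptive statistics only, so no test, model or covariate was fixed in advance there.

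**The concern.** The SAP adjusts for a baseline difference in comorbidity but does not name the baseline of the outcome itself. That value is the obvious candidate. The protocol collects it for every followed patient, and it bounds the outcome: a score cannot fall below 0, so the largest possible improvement equals the T1 score. On the NPI-NH total, entry needs only 1 point while the form allows up to 10 × 4 × 3 = 120, so starting points may differ widely. An area score can even be 0 at T1 in a patient who qualifies on the total.

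Analysing raw change fixes the slope on T1 at 1. When the true slope is below 1, two things usually follow. The estimate is noisier than it need be, and a chance T1 difference moves it in favour of the arm that started worse. For a small descriptive pilot the useful product is an effect estimate with its uncertainty, and this section shows no adjusted estimate.

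**Working it through.** The plan has no figure to reproduce: the documents give no SD, T1-T3 correlation, analysed N or regression estimate. Everything below is illustrative.

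**Inputs.** Planned enrolment is 16 per arm, N = 32 (protocol section 7). The analysed number may be lower, since "The withdrawn patients will not be evaluated unless they have been treated for 8 days" (section 5); 12 per arm is shown as an assumed smaller case. Assumed: within-arm correlation ρ between T1 and T3 of 0.3 to 0.8, and CIRS unrelated to the score.

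**Step 1, residual variance, equal SDs.** Change score: 2·SD²·(1 − ρ). After adding T1: SD²·(1 − ρ²). Ratio: (1 + ρ)/2.

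**Step 2, cost of the extra term.** With group and CIRS already in the model, adding T1 multiplies the variance on average by (N − 4)/(N − 5): 28/27 at 16 per arm and 20/19 at 12. Without CIRS the factor at 16 per arm is (N − 3)/(N − 4) = 29/28, and the equal-SD results at 16 per arm are the same to two decimals.

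**Step 3, unequal SDs.** With k = SD(T3)/SD(T1), the ratio before the factor is k²(1 − ρ²)/(k² + 1 − 2ρk). The last column uses k = 1.25.

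| ρ | (1 + ρ)/2 | 16 per arm | 12 per arm | 16 per arm, T3 SD 25% larger |
|---|---|---|---|---|
| 0.3 | 0.65 | 0.67 | 0.68 | 0.81 |
| 0.5 | 0.75 | 0.78 | 0.79 | 0.93 |
| 0.7 | 0.85 | 0.88 | 0.89 | 1.02 |
| 0.8 | 0.90 | 0.93 | 0.95 | 1.04 |

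**Step 4, break-even.** Setting (1 + ρ)/2 × 28/27 = 1 gives ρ = 2 × 27/28 − 1 = 0.93.

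**Step 5, simulation at 16 per arm with CIRS as noise in both models.** Normal scores, least squares: 0.68, 0.78, 0.88 at ρ 0.3, 0.5, 0.7. Lognormal scores (ρ before transformation): 0.64, 0.73, 0.81. Median regression on normal scores (800 runs, approximate): 0.71, 0.86, 0.90. None of these represents an area score with many zeros at T1.

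**Step 6, chance T1 difference.** The difference in T1 means has SD √(2/16) = 0.354 in units of the score SD. A gap of 0.5 SD or more therefore lies beyond 0.5/0.354 = 1.41 standard errors and occurs in about 16% of randomisations. With equal SDs such a gap shifts the difference in mean change by 0.5 × (1 − ρ): 0.35, 0.25, 0.15 or 0.10 SD at ρ 0.3, 0.5, 0.7 or 0.8.

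**Step 7, what the coefficient means.** If T3 − T1 = a + b·group + c·T1 + d·CIRS, then T3 = a + b·group + (c + 1)·T1 + d·CIRS with the same residuals. So b is identical in both forms, for least squares and for median regression, and remains a difference in change. The identity needs CIRS in both models or in neither.

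**The case against.** The best case for the SAP is that change from T1 is the protocol's own definition of improvement, that randomisation makes the comparison of changes valid, and that the regressions only support a Mann-Whitney test to which the variance ratios do not apply. All of that stands. With skewed scores a rank test can be more powerful than a regression with robust errors, so no power gain is claimed. It also stands that the benefit depends on unreported quantities and can vanish, as the 25% larger T3 SD shows, and that a T1 model chosen now is itself post hoc.

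Some stronger readings are tempting, and the documents do not support them:

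- A reader might infer that T1 was left out of the models. The section gives no full model list; it shows only that T1 is not named.
- A reader might infer that CIRS was certainly chosen from the data. This is a fair inference from the remark on its imbalance and its absence from the protocol, but the timing is not stated.
- A reader might infer that the estimates are withheld altogether. The SAP says they are not presented in that place, not that they appear nowhere.
- A reader might infer that the arms did differ at T1 and that the result is distorted. No T1 values by arm are available, so no actual shift can be claimed.

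**Conclusion.** The point holds as a modest improvement in precision and reporting for a supporting analysis, and is graded as something to consider. Calling the analysis biased or invalid would go too far: over randomisations the unadjusted change comparison is sound.

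With equal SDs at 16 per arm, the variance of the regression-based mean difference would be multiplied by about 0.67 to 0.93 for ρ from 0.3 to 0.8. At ρ = 0.5 the standard error falls by about 12% (√0.78 = 0.88). The gain disappears above ρ of about 0.93, or at ρ 0.7-0.8 if scores spread out by 25% between T1 and T3. These figures rest on assumed correlations and SDs and on planned rather than analysed numbers. That the scores are NPI-NH totals or areas is inferred from the protocol's visit schedule and the SAP's mention of an area.

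**What to change.** Keep CIRS and add the T1 value of the same score, total or area as analysed, to the existing linear and median regressions of T3 − T1 on group. Report the adjusted difference with a 95% CI, using small-sample robust errors such as HC3 for the linear model. Show it beside the Mann-Whitney result and the CIRS-only estimates, and give the analysed N and the T1 mean and SD per arm. Label the CIRS and T1 models post hoc. Extend this to staff distress only if it was also analysed as a T3-T1 change, which the SAP does not say.

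The cost is SAP wording, a re-run on data the protocol already collects, one degree of freedom and one more post hoc model. If the true T1 slope is 1, the added variance at 16 per arm averages 1/28 = 3.6% (1/27 = 3.7% with CIRS in the model).
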